# Identify the variables that contribute to vulnerability in children with suspected sepsis, during pandemic and non-pandemic times.

We will use descriptive statistics and standard statistical tests to compare the clinical, demographic and social factors of the pre-pandemic and pandemic cohorts. These include important identity factors such as gender, age, economic indicators, and geography. Multivariate models such as clustering algorithms and Principal Component Analysis will be used to further understand if and how the pre-and during-pandemic cohorts separate and differ.

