### Additional objectives due to the impact of COVID-19 at the study sites:

1. Develop data driven prediction models for identifying vulnerable children with suspected sepsis that are robust during future COVID-19 surges and novel pandemics.

- 2. Identify the variables that contribute to vulnerability in children with suspected sepsis, during pandemic and non-pandemic times.
- 3. Collect additional COVID-19 related prediction variables to inform understanding of the severity, risk factors, and clinical features of this disease at our three study sites (rural, urban and peri-urban).

**Objective B:** To validate the use of an automated Radio-Frequency Identification (RFID) method to track timeliness of interventions.

RFID tags will be small paper or plastic objects that can be attached to clothing or worn as a bracelet, anklet, or necklace (as preferred by child's caregiver) that use Bluetooth frequency band. The tag sends signals which allows tracking exactly where a patient is at a given time for analysis. For example, if a patient wearing an RFID tag enters a room, a reader in the room will detect the signal and add a timestamp for when patient was in the room. The Bluetooth frequency is no different to that used by mobile phones and is not expected to interfere with other processes in the hospital.

**Objective C:** To conduct an economic evaluation to contextualize our results for informing budgetary decisions of scaling-up Smart Triage.

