### Changes due to the impact of COVID-19:

We hypothesize that the case mix of the "pandemic period" cohort is likely to be different to the case mix seen during "non-pandemic" times. This includes a potential increase in the average severity of disease in those children presenting at the facility. We are requesting support for the addition of a pandemic phase in Phase 1 – the baseline observational component of PRST. This will include a 25% increase in sample size at each experimental site (250 additional participants per experimental site). This increase in sample size is critical to developing a risk stratification model that is robust during pandemic and non-pandemic times.

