# Methods: Data Collection, Management, and Analysis

# 15. Data Collection

### Predictors, Hospital Outcomes, 7-day Follow-up Calls

All study nurses will be trained and well versed on the standard operating procedures to facilitate standardization of all measurements. Study nurses will collect data using a custom-built Android application on a Samsung Galaxy Tablet A8. The list of predictors to be collected include clinical signs and symptoms, demographic/sociodemographic data, and pregnancy/birth information (see Appendix A). Similarly, designated study nurses will obtain hospital outcomes (see Appendix A) from patient records and enter them into the application on the Samsung Galaxy Tablet. Study nurses will conduct 7-day follow up calls in accordance with the standard operating procedures and enter the data into the application on the Samsung Galaxy Tablet.

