#### Additional Analyses due to the impact of COVID-19:

# Develop data driven prediction models for identifying vulnerable children with suspected sepsis that are robust during future COVID-19 surges and novel pandemics.

We will specifically look at the predictive performance of the model during this initial pandemic period (2-3 months) in comparison to following non-pandemic period. We will use traditional statistical modeling techniques (e.g. logistic regression) and data-driven algorithms (e.g. elastic net and random forest) to identify new predictors and calibrate existing predictors, exploring possible interactions between periods. We will validate the model using test sets that include both post-and during-pandemic data in order to ensure that any newly derived model performs consistently during both periods. Performance of prediction models will rely on area under receiver operating characteristics, and specificity corresponding to 80% sensitivity. Our goal is to develop a model for identifying those most at risk for sepsis that performs well despite changes in case mix of our cohort, even if this slightly degrades overall prediction performance. This will ensure that the final model will be more robust to future changes in case mix during future health crises.

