As we are continually collecting data regarding predictors for admission alongside the clinical team, there is the possibility that our research activities may interact with the efficiency of delivering the sepsis bundle of care. Although the possibility of such interaction is minimized by our use of dedicated research personnel who would not approach patients who are actively receiving clinical care, any such interactions could potentially limit the external validity of our study to non-researchcontrolled settings. Therefore, to assess this potential interaction, we will pause the collection of predictor data 1 month before and after implementation of the PRST program. This pause will also occur in the control group in order to replicate any bias caused by changes in our primary outcome attributable to the pause rather than the PRST program. To investigate the potential for this bias, we will treat the collection or non-collection of predictors as a dummy variable for subgroup analysis using the difference in difference in differences method described above.

All analyses will be conducted using R statistical software [25], and an alpha level of 0.05 will be considered statistically significant for all outcome analyses.

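### The COVID-19 objective to identify variables that contribute to vulnerability is assigned a between-period comparison with no outcome, which describes case mix and cannot show which factors raise risk in either period

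*Combined protocol and SAP*

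**What the plan says.** Protocol version 5.0, Section 6, lists as the second COVID-19 objective: "Identify the variables that contribute to vulnerability in children with suspected sepsis, during pandemic and non-pandemic times". Section 17 repeats this sentence as a subheading and plans the following under it: "We will use descriptive statistics and standard statistical tests to compare the clinical, demographic and social factors of the pre-pandemic and pandemic cohorts". Of the factors it says: "These include important identity factors such as gender, age, economic indicators, and geography". It then adds clustering and principal component analysis, to explore whether the two cohorts are distinct and in what way. The subsection gives no outcome, named test, alpha, number of variables, covariate adjustment or multiplicity method, and no exploratory label.

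Four other places bear on this:

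- **Section 17, preceding subsection (first COVID-19 objective).** Logistic regression, elastic net and random forest will be used "to identify new predictors and calibrate existing predictors, exploring possible interactions between periods". Performance is judged by the area under the ROC curve and by specificity at 80% sensitivity. The goal is a model that performs consistently when case mix changes.
- **Section 11.** Hospital admission within 5 days of assessment is the outcome for model development.
- **Section 13, COVID-19 changes.** "We hypothesize that the case mix of the 'pandemic period' cohort is likely to be different to the case mix seen during 'non-pandemic' times".
- **Section 7.** Phase I is split into a pandemic cohort (first 3 months) and a post- or non-pandemic cohort (latter 3 months).

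**The concern.** A variable contributes to vulnerability only in relation to something bad that happens to the child. The planned contrast asks a different question: is the factor more or less common among enrolled children in one period than in the other? The two questions can have opposite answers.

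Followed as written, the subsection would produce a list of factors whose prevalence shifted between two consecutive quarters. Under its heading, that list would be read as the variables that make children vulnerable. Factors that matter in both periods at a stable prevalence would be missing, as would factors whose effect changed while their prevalence did not. The published protocol's Discussion says the tool's performance may vary by season, so some of the shift may be seasonal and not due to the pandemic.

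**Working it through.** The plan states no test count, alpha or error rate for this analysis, so there is no figure to reproduce.

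**1. What each analysis estimates.** For a factor X in period t, let π(t) be its prevalence, and let r1(t) and r0(t) be the outcome risks with and without it.

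- The planned tests address π(pandemic) = π(comparison period).
- Contribution to vulnerability in a period concerns r1(t) against r0(t).
- A change in contribution concerns whether that contrast differs between periods.

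The second and third quantities do not involve π(t), so no test of π(t) informs them. Clustering and principal component analysis are multivariate, but they are unsupervised and aimed at the same cohort contrast. They add no outcome.

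**2. How far the answers can diverge (illustration).** Section 13 gives a Phase I minimum of 1,000 plus 250 further children per experimental site. The split by period is not stated, so I take 1,000 v 250 and 625 v 625. The prevalences and alpha = 0.05 are my assumptions.

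- *Factor unrelated to outcome, prevalence 30% then 40%.*
  - 1,000 v 250: SE = √(0.3×0.7/1000 + 0.4×0.6/250) = 0.0342; 0.10/0.0342 = 2.92; power ≈ Φ(2.92 − 1.96) = 83%.
  - 625 v 625: SE = √(0.21/625 + 0.24/625) = 0.0268; 0.10/0.0268 = 3.73; power ≈ Φ(1.77) = 96%.
- *Factor that strongly raises admission risk in both periods, prevalence unchanged.* It is flagged 5% of the time, by chance alone.

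The irrelevant factor is listed 83–96% of the time and the relevant one almost never.

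**3. Multiplicity (secondary).** A hand count of Appendix A gives about 50 items asked of every child and about 98 with branching items. The table is broken, so the count is approximate. No alpha is given for this analysis. I borrow 0.05 from the published protocol, where "an alpha level of 0.05 will be considered statistically significant for all outcome analyses".

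Expected false period differences = m × (1 − share truly different) × 0.05; this does not require independent tests.

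| Share truly different | m = 50 | m = 100 |
|---|---|---|
| 0% | 2.5 | 5.0 |
| 25% | 1.9 | 3.75 |
| 50% | 1.25 | 2.5 |
| 75% | 0.6 | 1.25 |

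If nothing differs and tests are independent, the chance of at least one is 1 − 0.95^50 = 92% to 1 − 0.95^100 = 99%; positive correlation lowers it. These are errors about period differences. Removing all of them would not answer the objective.

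**4. The comparator.** The subsection compares pre-pandemic with pandemic children. Section 7 defines pandemic and post- or non-pandemic cohorts, and the published protocol has recruitment starting in April 2020. No pre-pandemic cohort is described.

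**The case against.** The strongest reply is that the outcome analysis is already planned next door. The preceding subsection seeks new predictors with logistic regression, elastic net and random forest and explores period interactions, and Section 11 makes admission the model-development outcome. Identifying predictors of admission is a route to identifying vulnerability, so one could call the gap a missing cross-reference.

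Part of this stands. The plan does contain an outcome-based analysis, and the remedy is close to it. But that analysis serves a separate objective and is judged on discrimination. It promises no effect estimates by period, and the vulnerability subsection does not refer to it. A penalised or tree-based model chosen for robustness can drop or blur the very variables whose effect differs by period.

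It is also fair to say that this is an added objective outside the primary outcomes, that the wording is partly descriptive, and that no decision hangs on these p-values. That limits the consequences and is why multiplicity comes second.

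Three stronger readings are tempting but not supported:

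- *The tests are unadjusted.* The subsection is silent on adjustment; it does not rule it out.
- *Univariate tests are the whole plan.* Clustering and principal component analysis are also planned.
- *The plan will yield 3 to 5 falsely identified vulnerability variables (60 to 100 tests at 0.05).* This needs an assumed test count, an alpha stated only for outcome analyses, and no true difference anywhere, which Section 13 contradicts. It also needs a rule that significance identifies a vulnerability variable, and the plan states none.

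**Conclusion.** The concern holds as a mismatch between objective and analysis. This rests on the text alone: the objective concerns what contributes to vulnerability in each period, and the subsection meant to answer it names no outcome. It does assume that vulnerability means risk of a poor outcome. The documents do not define the term, but they tie model development to need for admission, and the objective covers non-pandemic times too, which a between-period contrast cannot address.

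The error-control point is minor and conditional: an upper limit of about 2.5 to 5 expected false period differences for 50 to 100 tests at 0.05, falling to about 1.25 to 2.5 if half the factors truly differ. The undefined pre-pandemic cohort is a separate inconsistency in the same paragraph. The change should be made; it does not touch the primary effectiveness analysis.

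**What to change.** Rewrite the subsection in Section 17 as follows.

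1. Name the vulnerability outcome: admission as defined in Section 11, and death where events allow.
2. Using the modelling framework of the preceding subsection, model that outcome on the candidate variables, period and variable-by-period interactions. Report period-specific effects as well as interactions, with 95% confidence intervals, because the objective covers both periods.
3. Label the analysis exploratory. If variables are to be declared identified, state the family of tests and a false-discovery procedure.
4. Present the between-period comparison, clustering and principal component analysis as descriptive case-mix summaries, for example with standardised differences.
5. Reconcile the pre-pandemic comparator with the cohorts in Section 7.

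The cost is a paragraph of text and a little extra analysis; no new data are needed. Interaction estimates will be imprecise. At the 12% admission rate of Section 13, a pandemic cohort of 250 at one site gives 250 × 0.12 = 30 admissions and one of 625 gives 75. By the plan's own 10-events rule that supports about 3 to 7 variables per site, which argues for penalisation, pooling across sites where justified, or a short pre-selected list. Fewer variables will be declared identified. Season will still be mixed with period and should be stated as a limitation.

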#### **Economic Evaluation**

We will conduct a cost-effectiveness analysis of Smart Triage by calculating the cost per averted year of life lost (YLL) using decision analysis. Previous models (21) and expert opinion has been consulted for potential pathways of healthcare utilization. We will model uncertainty using probabilistic sensitivity analysis and will take a societal perspective as our base case.

Probabilities of healthcare utilization will be calculated via primary data from the Smart Triage case report form. The primary outcome of "time to bundle of care" will be linked to mortality via existing evidence (22) as required in order to calculate YLL, as Smart Triage was not originally powered to detect mortality. We will use the World Health Organization's life expectancy data in Uganda (23) to calculate projected YLL before and after program implementation. Costs of healthcare utilization is available through existing literature (21, 24), and indirect costs due to lost wages will be gathered as primary data in Smart Triage. Costs of program setup and maintenance will be tracked from study expenses and incorporated into the analysis.

To contextualize our results for informing budgetary decisions of scaling-up Smart Triage, we will estimate a projected budget impact of scale up given the disease burden of pediatric sepsis in Uganda (25), as recommended for newly proposed healthcare programs (26). The results of this preliminary budget impact analysis can be refined in further multicenter trials and can be compared to that of other programs to facilitate healthcare resource allocation in Uganda.

# **Methods: Monitoring**

18. Data Monitoring

Internal monitoring of study processes will be done regularly by the Study Coordinators at each hospital site. During monitoring, data and consent forms for 10% of enrolled participants will be reviewed for compliance. Retraining of study staff will be done to correct for any inconsistencies noted during monitoring and follow-up will be subsequently done by the Study Coordinator to ensure compliance.

Data completeness will be continuously monitored using daily, weekly and monthly reports. Accuracy of data will be verified using an audit of 5% of cases by a Data Manager who will not be involved in enrolling subjects. Preliminary data quality checks and analysis will be performed throughout the data collection stage to ensure that data collected is valid and secure. These data quality checks will include checking the quality of pulse oximetry waveform data via implementing a Signal Quality Index (SQI) algorithm and checking for completeness and validity of input data. Further data quality checks will inspect the number of patients enrolled, the number of patients admitted, and the timed outcome data. Upon completion of data collection, a summary of the data collected will be compiled and will be discussed by the investigators and the study nurses to ensure that data is clean, correct and useful.

### 19. Harms

We do not anticipate any adverse events directly attributable to the study. The most significant risk in this study is a small delay in treatment administration due to incorrect triage by the digital triage tool. However, this delay would not be significantly different from the hospital standard of care. The risk of an adverse event is unlikely because our digital health intervention will only be used to triage participants, and all subjects will be assessed by a healthcare provider regardless of triage status.

All children enrolled into this study will receive standard care according to local, regional and national guidelines. No study procedures will take place which in any way interfere with the prescribed care. Study procedures will be delayed, when necessary, to ensure that these procedures will not impact recommended care.

# **Ethics and Dissemination**

### 20. Research Ethics Approval/Protocol Amendments

Ethical approval will be sought from Makerere University School of Public Health (MUSPH) Higher Degrees, Research and Ethics Committee. Ethical approval will also be obtained from from the Kenya Medical Research Institute (KEMRI) Scientific & Ethics Review Unit (SERU), and from The University of British Columbia/ Children's and Women's Health Centre of British Columbia Research Ethics Board (UBC C&W REB). A copy of the protocol proposed informed consent forms, other written participation information, and any proposed advertising material will be submitted for written approval. The investigators will submit and, where necessary,

obtain approval from the IRB/IEC for any major protocol amendments and changes to the informed consent document. The study team are responsible for assuring that this protocol and the associated informed consent documents and study-related documents are approved prior to implementation of the protocol. Any major amendments to the protocol, informed consents, or other study- related documents must be approved by the IRB/IEC prior to implementation.

# 21. Informed Consent and Assent

The study nurses will be responsible for screening and consenting participants. This would be the norm in Kenya and Uganda. The Study Nurses will be certified and trained to ensure that the caregiver has a complete understanding of the consent processes, the consent form, and that the caregiver is of legal age and competent to provide consent.

In obtaining and documenting informed consent, the site investigators and their designees will comply with applicable local and domestic regulatory requirements. This clinical study will have a paper-based informed consent form (ICF) for enrollment developed for local use that are in accordance with applicable guidelines. The consent form will include the purpose of the study, a description of the procedures to be followed and the risks and benefits of participation. The informed consent process will give individuals all of the relevant information they need to decide whether to participate, or to continue participation, in this study. Potential research participants' caregivers will be encouraged to ask questions and to exchange information freely with the study team. Participants will be informed on who to contact (Principal Investigator) should they have any questions during, or after the study period. If the caregiver providing consent is illiterate, an independent witness will be present to verify to the caregiver that all the information read aloud is contained in the ICF. In this instance, both the caregiver and witness will sign the ICF. The caregiver will voluntarily sign, thumbprint and date (thumbprint acceptable if illiterate who will also require a witness) the consent form if they wish to participate in the study and will be provided with a copy of the consent form. A signed and dated copy of the consent form will be kept in the documentation file at all times.

In emergency cases, consent will be deferred until the child is stable and study procedures will only begin after initiation of emergency treatment. Study procedures will not delay or interfere with access to standard care. If consent is not granted, the data will be deleted. This deferred consent procedure is to avoid introduction of bias by neglecting to obtain data from the most severely ill children while avoiding delays in providing care to the child. This procedure has been used in previous studies involving children with severe illness, including use by the Fluid Expansion As Supportive Therapy (FEAST) study [27].

There will be separate consent forms for Phase I (Appendix F) and Phase III (Appendix G). Assent will be sought for children aged 13 and older (Appendix H). Consent will also be sought for participation in usability testing initiatives (Appendix I), the Triage Tool Training Questionnaire (Appendix J), and the Hospital staff Interviews (Appendix K). In addition, there will be separate consent forms for Kenya and Uganda as site specific guidelines differ (see

Appendices F to K). All consent materials will be approved by the appropriate Institutional Review Boards prior to use.

